5.2 Secondary Endpoints

Secondary endpoints are exploratory and do not have specific performance criteria requirements.

5.3 General Methodology

Unless otherwise stated, continuous variables will be summarized by number of observations, mean, standard deviation, median, minimum and maximum values, and categorical/dichotomous variables will be summarized using frequency tables (frequencies, percentages, confidence intervals).

Hypothesis tests of continuous variables will be based on two sample t-tests. Non-parametric Wilcoxon signed rank test may be used when underlying data are found to be non-normal.

Hypothesis tests of categorical variables will be based on a Chi-square (or Fisher exact) test.

Level of significance (α), for purposes of statistical comparisons/tests, will be 0.05.

6. Safety Evaluation

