10 STUDY VISIT PROCEDURES

The Schedule of Events is presented in Appendix A. A detailed description of assessments performed at each study visit is presented below.

Visit 1 (Day 0): Screening and Enrollment

The ASSURE System Training Manual provides detailed instructions for WCD fitting, programming, and System power ON. The following process will be followed at Visit 1.

- Review eligibility criteria
- Explain the purpose and conduct of the study visits to the subject, answer the subject's questions, and obtain written informed consent. This consent process can be performed in advance of Visit 1 at the discretion of the site Investigator.
- Provide the subject with a copy of the signed informed consent
- Obtain demographic data
- Collect ICD Baseline Documentation:
 - Perform a full interrogation of the ICD on the Day of enrollment prior to WCD garment fitting.
 - Synchronize the ICD internal clock to the current time and time zone.
 - If current programmed parameters do not include detection as low as 150 bpm, the Sponsor requests that a monitoring zone at 150 bpm be programmed at the approval of the subject's physician. (ICD data will be used to identify WCD Missed Events (False Negative Detections)).
 - Print the ICD report as part of the source documentation. The report shall include the programmed parameters and arrhythmic episode history.
- Obtain abbreviated limited medical history as specified in the Case Report Form (CRF).
- Perform Wearability Assessment as specified in the CRF. If there is any question regarding skin condition e.g. eczema, the site investigator shall use medical judgement to determine if it disqualifies the subject from participating.
- Obtain urine pregnancy test for women of childbearing potential. If positive, subject is ineligible to participate.
- Perform subject training, including overview of study procedures, hands-on assembly and disassembly of the garment and cable assembly, use and care of the

WCD, and review of manuals. Sponsor representative(s) may be available to assist.

- Have the subject complete the BORG Comfort Scale before they are fit with the Garment. This provides a baseline comfort level to which the follow up BORG Scale scores (obtained at Visit 2 after the subject has worn the WCD) can be compared.

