2.1 Study Design/Overview

The ASSURE WCD Clinical Evaluation – Detection and Safety Study (ACE-DETECT) is a multicenter single arm open label evaluation. All subjects will be fitted with the WCD and will be trained and provided written instructions for use, including safety precautions and adverse event reporting. Demographic data and limited medical history data will be collected. The subjects will be asked to complete a BORG Comfort Scale at Visit 1 (baseline). Subjects will wear the device for approximately 30 days during normal daily activities including sleep. Research Coordinators will conduct weekly phone interviews with the subjects during the participation period to address subject questions, review potential adverse events, and review usage. Subjects will return for a final visit, Visit 2, at the end of the wear period. At Visit 2 subjects will be interviewed regarding any adverse events they may have experienced since the most recent phone follow-up and the status of any adverse events that were recorded during the participation period. They will also be asked to complete a device usability survey and the BORG Comfort Scale after the device is removed. All episodes recorded by the ASSURE WCD, the subject's ICD, or other devices when available, will be reviewed by independent clinical experts.

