4.4 Subgroup Analyses

Subgroup analyses based on, but not limited to, gender, age, BMI and baseline QRS width will be provided on the primary effectiveness endpoint. These analyses will be regarded as exploratory, and have been selected for the following reasons:

- Gender The ASSURE WCD is available in two styles (male and female). Garment fit may influence false alarm performance.
- Age Higher levels of activity may be associated with higher levels of noise, and activity levels
 may be influenced by age. Subgroups will be based on a cutoff point of 75 years (<75/≥75).
- BMI Data presented previously on the LifeVest suggest that obese subjects experience a significantly higher percentage of noise, which may influence false alarm performance. (Wan C et al. ESC 2013. The impact of body mass index on wearable cardioverter defibrillator efficacy. Abstract P4926 Poster.) Subgroups will be based on a cutoff point of 30 (</≥ 30).
- QRS width Variable used for rhythm classification in the ASSURE WCD detection algorithm.
 Subgroups will be based on a cutoff of 120 ms (</≥ 120).
- ICD Device Type Subjects are eligible for enrollment with either a single or dual chamber ICD. Identification of Episode Rhythm type may be facilitated by the presence of a dual chamber ICD.

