7.1 BORG Comfort Scale

The BORG Comfort Scale consists of eight questions that ask the subject to check the number that best describes the level of discomfort the subject feels in each area of the body: upper right chest, upper left chest, lower right chest, lower left back, upper right back, lower left back and lower right back. The response options range from 0 (None at all) to 10 (Very, Very Severe). For the purpose of summarizing the BORG Comfort Scale, the data will be considered continuous and will be summarized at relevant visit intervals, including change from baseline.

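### SAP 5.3 pairs an independent-groups t-test with a paired-data rank test as its fallback, so one of the two is wrong for any continuous comparison tested under it

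*SAP*

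**What the plan says.** SAP 5.3 gives the only general rule for testing continuous variables. It states the default and an optional alternative together: "Hypothesis tests of continuous variables will be based on two sample t-tests. Non-parametric Wilcoxon signed rank test may be used" if the data are found to be non-normal. The level is also set there: "Level of significance (α), for purposes of statistical comparisons/tests, will be 0.05". Sidedness is not stated in that section.

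The study is a "multicenter single arm open label evaluation" (SAP 2.1), so there is no parallel treatment group. The data structures to which a continuous test could apply are these:

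- **Within-subject measures.** The BORG scale is completed at Visit 1 before the garment is fitted and again at Visit 2. Protocol section 10 gives the reason: "This provides a baseline comfort level to which the follow up BORG Scale scores" from Visit 2 can be compared. SAP 7.1 says that "the data will be considered continuous and will be summarized at relevant visit intervals, including change from baseline". Weight is also taken at both visits, since only height is dropped at Visit 2 (Protocol section 11, Wearability Assessment).
- **Independent groups.** SAP 4.4 states: "Subgroup analyses based on, but not limited to, gender, age, BMI and baseline QRS width will be provided on the primary effectiveness endpoint". It adds ICD type to the list and calls these analyses exploratory.

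SAP 4.3 places BORG among other measures for future consideration, outside the primary and secondary endpoints. SAP 5.1 gives the primary endpoint its own method (random-effects Poisson regression, with a bootstrap alternative) and adds an exploratory Poisson model with age, gender, BMI, QRS width and ICD type as covariates.

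**The concern.** A two-sample t-test compares the means of two independent groups. A signed-rank test assesses the location of within-subject differences, or of one sample against a fixed value. The non-parametric partner of the first is the rank-sum test; the parametric partner of the second is the paired t-test. SAP 5.3 takes one test from each pair, so an analyst who follows it literally meets one of two problems:

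- For a before-after measure, the default treats the two visits as separate groups of people and uses the wrong standard error.
- For two independent groups, the default fits the structure, but the prescribed alternative for non-normal data cannot be applied.

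At stake is the correctness of supportive tests, and whether the choice between tests is settled before the data are seen.

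**Working it through.** **Figure to reproduce.** None. SAP 5.3 and 7.1 state no sample size, power or error rate for these tests. The check is a matching of tests to data structures, followed by an illustration of size.

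**Step 1: match tests to structures.**

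| Comparison | SAP 5.3 default (two-sample t) | SAP 5.3 fallback (signed-rank) | Partner not named |
|---|---|---|---|
| Same subjects, two visits (BORG, weight) | does not fit: ignores pairing | fits | paired t-test |
| Two independent groups | fits the structure | cannot be used | rank-sum test |

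Each row has one misfit.

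**Step 2: the default on paired data.** Let σ₁ and σ₂ be the SDs at the two visits, r the within-subject correlation and n the number of pairs.

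- True variance of the mean change: (σ₁² + σ₂² − 2rσ₁σ₂)/n
- Variance used by the two-sample test: (σ₁² + σ₂²)/n
- With σ₁ = σ₂, the ratio of standard errors is 1/√(1−r)

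The documents give neither r nor the SDs, so both are assumptions here.

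| r (assumed) | 1/√(1−r) | Excess in standard error |
|---|---|---|
| 0 | 1.00 | none |
| 0.3 | 1.20 | 20% |
| 0.5 | 1.41 | 41% |
| 0.7 | 1.83 | 83% |

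Unequal SDs reduce the excess. If one SD is half the other and r = 0.5, the ratio is √[(1 + 4)/(1 + 4 − 2)] = √(5/3) = 1.29. Unequal SDs are plausible, because the baseline score is taken before fitting on a scale that starts at 0.

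**Step 3: effect on a test.** Simulation with 130 complete pairs (the minimum enrollment in SAP 4.2), normal data, equal SDs, two-sided 0.05, an assumed shift of 0.25 SD for power, and 20,000 replicates.

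| r | Type I error, two-sample | Type I error, paired | Power, two-sample | Power, paired |
|---|---|---|---|---|
| 0 | 0.049 | 0.050 | 52% | 52% |
| 0.3 | 0.019 | 0.047 | 52% | 67% |
| 0.5 | 0.006 | 0.051 | 53% | 81% |
| 0.7 | 0.001 | 0.053 | 53% | 95% |

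With positive correlation the default is conservative and loses power. It does not produce false positives.

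**Step 4: the fallback on independent groups.** With 130 subjects and the protocol minimum of 35 of one sex, the sex groups could be 130 − 35 = 95 and 35. A signed-rank call on 95 against 35 values fails because there are no pairs. Equal group sizes would not help: subjects in different groups have no natural partner.

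**The case against.** The strongest reply is that no analysis in the plan actually runs into this error, and most of that reply stands.

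- **BORG.** A reader might infer that the SAP prescribes the wrong test for BORG. It does not. SAP 7.1 commits only to summaries, including change from baseline. The protocol's statement that the scores can be compared is met by a descriptive change score. SAP 5.3 says what to use if a continuous variable is tested; it does not order a BORG test. If BORG were tested and found non-normal, the fallback would be the right test.
- **Subgroups.** A reader might infer that non-normal subgroup comparisons have no valid method. The planned subgroups concern the false-alarm rate, and SAP 5.1 has a Poisson covariate model with the same five factors. That suits a count with an assumed variance-to-mean ratio of 14 (SAP 4.2) better than a t-test would.
- **Intervals.** A reader might infer that confidence intervals are affected too. SAP 5.3 lists intervals only for categorical variables.
- **Size.** The inflation figures rest on an assumed correlation and equal SDs, and vanish at r = 0.

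What the reply does not remove is the rule itself. SAP 5.3 is the only general instruction for testing continuous variables, and no reading makes its two tests counterparts.

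**Conclusion.** SAP 5.3 is wrong as written, whatever becomes of BORG, because it joins tests for two different data structures. The consequence is conditional and minor: it arises only if a continuous variable is tested under 5.3. The default would then overstate the standard error of a within-subject change, by nothing at r = 0 and by 41% at r = 0.5 or 83% at r = 0.7 under equal SDs, and by less if the SDs differ. The direction, given positive correlation, is towards missing a real change in comfort; the descriptive change would still be reported. For independent groups the fallback is unusable. The primary analysis, the sample size and the success criterion do not depend on this section, and the secondary endpoints are exploratory (SAP 5.2). This is a correction worth making, not a threat to the study's conclusion.

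**What to change.** Replace the two sentences in SAP 5.3 with:

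> Within-subject change (e.g. BORG), if tested, will use a paired t-test, or the Wilcoxon signed-rank test if non-normal. Comparisons of continuous variables between independent groups will use a two-sample t-test, or the Wilcoxon rank-sum test if non-normal. False-alarm rates will be compared between subgroups with the Poisson model of section 5.1.

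The last sentence keeps the t-test rule from being extended to false-alarm counts. In SAP 7.1, add one clause stating whether BORG change is tested or only described.

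The cost is a few sentences in an amended SAP, with no change to endpoints, data collection or sample size. Under SAP section 9 the amendment must be approved before the primary endpoint is analyzed. After that, a change of test has to be reported in the clinical study report with its reason.

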6.1 Safety Endpoints

All adverse events that occur during the study will be recorded per the protocol definitions. Per the study protocol, adverse event (AE) is defined as any untoward medical occurrence in a subject during the study that in the opinion of the investigator is at least possibly-related to use of the ASSURE WCD System. For each AE, the Investigator will assess the causality/relationship to the study device (ASSURE™ WCD) and categorize the AE as mild, moderate, or severe, depending on the event's impact on the subject's daily activity level.

Adverse events occurring during the study will be tabulated by type, seriousness, severity, and relationship to the study device. The Medical Monitor assigned to this study will review the adverse events to determine whether any are reportable as UADEs. The Medical Monitor will also review serious adverse events to verify relatedness and the seriousness classification. The Medical Monitor's assessment of seriousness and relatedness, rather than the investigator's assessment, will be used for summarizing and analyzing safety data.

Any deaths or serious device associated AEs will be summarized. AEs leading to subject withdrawal from the study will be listed separately. In cases where the same event is reported more than once per subject, the event will only be counted once in the incidence tables. A listing of all adverse events will be provided.

7. Measurement Scales and Subject Reported Outcomes

7.1 BORG Comfort Scale

The BORG Comfort Scale consists of eight questions that ask the subject to check the number that best describes the level of discomfort the subject feels in each area of the body: upper right chest, upper left chest, lower right chest, lower left back, upper right back, lower left back and lower right back. The response options range from 0 (None at all) to 10 (Very, Very Severe). For the purpose of summarizing the BORG Comfort Scale, the data will be considered continuous and will be summarized at relevant visit intervals, including change from baseline.

7.2 Device Usability Survey

The subject will be asked to complete the Device Usability Survey at Visit 2 after the Garment is removed. The survey consists of ten questions and ask the subject to indicate the level of agreement or disagreement with each of the questions, based on five response options: Strongly Disagree, Disagree, Neutral, Agree and Strongly Agree. The responses to the ten questions are summed for each survey and then multiplied by 2.5 to convert the original scores of 0-40 to 0-100. The usability scores will then be analyzed as a continuous measure.

8. General Statistical Methods

8.1 Missing Data

All reasonable efforts will be made to ensure complete and accurate data are collected on all enrolled subjects as set forth in the protocol and CRFs. Subject WCD wear-time, and the associated heart monitoring during wear-time, however, do not lend themselves to imputation in the case where data are found to be missing, for any reason, and no efforts will be made to do so. Any extended periods of absence of WCD wear-time and/or and heart monitoring will be investigated for cause.

8.2 Analysis Sets

- The Intent-to-Treat (ITT) set of subjects will include the data from all enrolled subjects. No subjects will be excluded from this data set for any reason (e.g., protocol violation, study device not used, etc.).
- The Per Protocol (PP) set of subjects will include all subjects enrolled who met the eligibility criteria and were appropriately fitted with a WCD (correct Garment size based on the sizing chart in the ASSURE System Training Manual). The determination of subjects excluded from the PP set will be made prior to locking the final database.
- The Safety (SAF) set of subjects will include all subjects who used the device for at least two hours. No subjects (or data) will be excluded from this dataset because of protocol deviations that occur during the study.

The primary endpoint analysis will be based on the ITT dataset, although a secondary analysis may also be performed based upon the PP dataset (if there are differences), to assess the sensitivity of the analysis to the choice of analysis dataset. The analyses of all other endpoints will be based upon the ITT dataset only. All safety analyses will be based upon the Safety dataset.

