9 GENERAL STUDY PROCEDURES

Screening

Research Coordinators (RCs) will work in conjunction with the site investigators to identify patients who meet eligibility criteria at their respective site. Candidates will be initially screened either in person or by phone. For eligible candidates who express interest in participating, a Screening and Enrollment Visit will be scheduled (Visit 1). These candidates may be provided a copy of the informed consent along with supplemental materials that illustrate the device to review prior to Visit 1.

Enrollment and Screen Failures

At Visit 1, subject eligibility will be reviewed. Subjects who are still eligible and have provided written informed consent by signing the Informed Consent Form (ICF) will be considered for enrollment. Subjects will be provided a copy of the signed ICF.

Subjects will be considered enrolled in the study when they have completed training, are successfully fitted with a WCD System, the Monitor is connected to the Garment and the System is powered ON. Subjects who are consented but not enrolled per this definition will be classified as screen failures.

Subject Identification Numbers

Each enrolled subject will be assigned a unique subject identification (SID) number. The first three characters of the SID will reflect the study site number (e.g. S01, S02, ..., S10). The Sponsor will inform each site of its designated site number before the site is opened for enrollment. The last two digits will be assigned based on the enrollment sequence (e.g. the first subject enrolled at each site will be assigned 01) and will be separated from the site designation by a hyphen e.g. S01-05 is subject 05 enrolled at site 01. This number will be used on the Case Report Form (CRF) and on the CareStation website data uploads. The Sponsor will not collect Protected Health Information that would allow specific subject identification (e.g. date of birth, name, initials, medical record number) on the CRF or in the WCD system data.

Unscheduled Visits

Unscheduled visits may be necessary due to AEs or other reasons. The Investigator may examine a subject as often as is medically necessary while the subject is enrolled in the study. Assessments performed at unscheduled visits are at the discretion of the Investigator and will be documented in the CRFs.

Phone Calls

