Adverse events (AEs) as defined below will be monitored continuously during the study from the time the subject is considered enrolled through resolution. Subjects will be instructed to report all AEs during the study, and study personnel will interview the subjects regarding new AEs during each weekly phone call follow up. AEs may be reported by the subject, discovered by Investigator questioning, or detected through physical examination or other means at the study exit visit.

Device Usability Survey

A device Usability Survey will be administered at Visit 2.

Definitions

For the purposes of this study, an **AE** is defined as any untoward medical occurrence in a subject during the study that in the opinion of the investigator is at least possibly-related to use of the ASSURE WCD System.

A serious adverse event (SAE) is defined as any adverse event that:

- Leads to death
- Leads to serious deterioration in the health of a subject that:
 - Results in a life-threatening illness or injury, or
 - Results in a permanent impairment of a body structure or a body function, or
 - Requires in inpatient or prolonged hospitalization \geq 24 hours, or
 - Results in medical or surgical intervention to prevent life-threatening illness or injury or permanent impairment to a body structure or function, or
 - Leads to fetal distress, fetal death or a congenital anomaly or birth defect.

Adverse Device Effect (ADE) is an adverse event related to the use of an investigational medical device.

Anticipated Adverse Device Effects (AADE) are those events related to the use of the device that are reasonably expected to occur as a result of the subject's participation in

the study. The following are AADEs based on results from the series of previous feasibility studies listed in Section 6 and the system engineering hazard analysis:

- Mild to moderate skin irritation
- Muscle Strain
- Emotional discomfort e.g. anxiety, uncomfortable or claustrophobic feelings
- Fall Injury
- Bruising
- Pinched Fingers
- Shoulder discomfort
- Skin Infection (bacterial or yeast)
- ICD System Infection

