An **Unanticipated Adverse Device Effect (UADE)** is any serious adverse effect on health or safety or any life-threatening problem or death caused by, or associated with the device, if that effect, problem, or death was not previously identified in nature, severity, or degree of incidence in this protocol; or any other unanticipated serious problem associated with the device that relates to the rights, safety, or welfare of subjects.

All AEs will be assessed by the investigator according to:

- Whether the event is serious (SAE);
- The severity of the event (mild, moderate, severe); and
- The relationship of the event to device use (possibly, probably, or definitely related)
 - Possibly Related There is a reasonable possibility that the AE may have been primarily caused by device use. The AE has a reasonable temporal relationship to the use of the device and follows a known or expected response pattern to device, but alternative etiology is equally or more likely compared to the potential relationship to the use of the device.
 - Probably Related There is a reasonable probability that the AE may have been primarily caused by device use. The AE has a reasonable temporal relationship to the use of the device and follows a known or expected response pattern to device. Note: this definition assumes no

alternative etiology is equally or more likely compared to the potential relationship to the use of the device.

 Definitely Related – The AE has a strong causal relationship to device use. The AE follows a strong temporal relationship to the use of the device, follows a known response pattern to the device, and cannot be reasonably explained by known characteristics of the subject's clinical state or other therapies.

Whenever possible, the Investigator should group signs or symptoms that constitute a single diagnosis under a single AE term (e.g. redness and swelling can be combined under skin irritation).

Baseline conditions e.g. mild eczema, and AEs identified at Visit 1 following enrollment will be documented during the Wearability Assessment. Baseline conditions are not considered adverse events unless the condition worsens because of study device use.

Adverse Event Reporting Procedures

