12 STATISTICAL OVERVIEW

Data Sources

Outcome measures for the primary and secondary endpoints will be obtained by boardcertified electrophysiologist review of Episodes recorded during the study period by the subject's ICD and/or the ASSURE WCD per the definitions and instructions identified in the *Endpoint Review Committee (ERC) Charter for ASSURE WCD Clinical Evaluation - Detection and Safety Study (ACE-DETECT)* (3334131). Cumulative wear time, which is also required to calculate the primary endpoint is recorded by the ASSURE WCD as "Usage" data and accessible via the CareStation website. The estimated inappropriate shock rate will be calculated as the product of the False Positive Alarm Rate (primary outcome measure) and the missed shock alarm rate obtained from prior usability studies (described in Section 6) conducted by the sponsor.

Determination of Sample Size

The sample size for this study is determined based on the primary endpoint.

Approximately 130 subjects will be enrolled. It is anticipated that 10 sites will participate and that a maximum of 18 subjects will be enrolled at each site. This sample size will provide approximately 90% power, at a significance level of 2.5%, to detect a difference between the study false alarm rate and the comparator rate if the true false alarm rate for the study device is at least 50% lower than the comparator rate. Power was calculated using the R statistical package. The comparator rate was chosen to be 0.29 false alarms per subject-day (one alarm every 3.43 days), which is the performance reported for the currently marketed ZOLL LifeVest® Model 3000⁴. A more detailed description of this calculation is provided in the Statistical Analysis Plan (SAP) (3338311).

Data sets to be analyzed

The primary and secondary endpoints will be analyzed using the Intent-to-Treat (ITT) and Per-Protocol (PP) sets of subjects, and all safety variables will be analyzed using the Safety (SAF) set of subjects. These data sets are defined below. Additional data sets may be defined in the Statistical Analysis Plan (SAP).

⁴ LifeVest Model 3000 Clinical Study (as reported in LifeVest 4000 operator's manual pg. 7-5.)

- The ITT set of subjects will include the data from all enrolled subjects. No subjects will be excluded from this data set for any reason (e.g., protocol deviation, study device not used, etc.).

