- The PP set of subjects will include all subjects enrolled who met the eligibility criteria and were appropriately fitted with a WCD (correct Garment size based on the sizing chart in the ASSURE System Training Manual). The determination of subjects excluded from the PP set will be made prior to locking the final database.
- The SAF set of subjects will include all subjects who used the device for at least two hours. No subjects (or data) will be excluded from this data set because of protocol deviations that occur during the study.

Subject Disposition

Subject disposition including the number of subjects enrolled and number of subjects completing the study (and completing each study visit) will be tabulated. The percentage of subjects completing the study will be based on the total number enrolled. Protocol deviations will also be summarized. Subject withdrawals and the reasons for withdrawal will also be summarized.

Analysis of Demographic and Baseline Data

Subject demographic and baseline data will be summarized by treatment arm for the ITT set of subjects. Continuous variables will be summarized using descriptive statistics (number of subjects, mean, standard deviation, median, minimum and maximum), and categorical variables will be summarized using the count and percentage of subjects in each category.

Endpoint Analysis

It is planned that the data from all clinical sites that participate in this study will be combined, so that the target sample size will be available for analysis. Further details of the statistical methods will be included in the Statistical Analysis Plan (SAP).

The primary endpoint in this study will be based on the assessment of performance in comparison to published performance for a comparative currently marketed device.

The endpoint analyses will be performed after all subjects have either completed the final visit or withdrawn early from the study, the study database has been cleaned, verified and locked, and adjudication/reconciliation of all Episodes is complete as specified in the Episode Annotation Protocol for *ASSURE WCD Clinical Evaluation* - *Detection and Safety Study ACE - DETECT* (GDR 3334131).

Alarm Definitions (for the Primary Endpoint)

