An estimate of the inappropriate shock rate will be calculated as the product of the WCD False Positive Alarm Rate (the Primary Outcome measure of this study) and the Missed Shock Alarm Rate. The Missed Shock Alarm Rate was derived from two prior studies during which high priority alarms (shock alarms) were delivered randomly to study subjects. A "Missed Shock Alarm" was one during which the subject failed to respond to the shock alarm within 20 seconds following alarm activation. Data was obtained both during sleep (GDR 3333597 ASSURE UISim Sleep Study) and during normal daily activities (GDR 3334121 ASSURE UISim 7-day study).

Adverse Events

AEs will be summarized using the SAF subject set. Separate summaries of AEs at least possibly related to device use and by severity (as reported by the Investigator and reviewed by the Medical Monitor) will be prepared. UADEs will also be summarized. AEs leading to withdrawal from the study will be listed and tabulated.

Subgroup Analysis

Subgroup analyses are exploratory and will be specified in the Statistical Analysis Plan.

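### Protocol and SAP conflict on which subjects enter the adverse event tables: a Safety set requiring two hours of device use, or everyone enrolled at power-ON

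*SAP*

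**What the plan says.** **Threshold.** SAP 8.2: "The Safety (SAF) set of subjects will include all subjects who used the device for at least two hours". Protocol 12 (Data sets to be analyzed) agrees: "The SAF set of subjects will include all subjects who used the device for at least two hours". Neither says whether the two hours are cumulative or continuous, and neither gives a reason for the threshold.

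**Use of the set.** Protocol 12 states that "all safety variables will be analyzed using the Safety (SAF) set of subjects" and, in its Adverse Events paragraph, that "AEs will be summarized using the SAF subject set". SAP 8.2 likewise puts all safety analyses on the Safety dataset.

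**Start of AE observation.** Under Protocol 9 a subject is enrolled once trained and fitted, when "the Monitor is connected to the Garment and the System is powered ON". Protocol 11 says AEs are "monitored continuously during the study from the time the subject is considered enrolled through resolution". It also foresees very early events: "AEs identified at Visit 1 following enrollment will be documented during the Wearability Assessment".

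**Text pointing to a wider population.**
- SAP 4.5 has every AE reported during the study summarized and tabulated, with no use threshold.
- SAP 8.3 keeps the data that withdrawn subjects contributed before withdrawal in all analyses.
- SAP 8.2 assigns endpoints other than the primary to ITT only, and device-related AEs are a named secondary endpoint (Protocol 8, SAP 4.3). Protocol 12 has a similar overlap: secondary endpoints on ITT and PP, safety variables on the Safety set.

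**The concern.** A device can cause harm as soon as it is put on. Protocol 11 lists pinched fingers, anxiety or claustrophobic feelings and shoulder discomfort among the anticipated device effects, and these could plausibly arise soon after fitting. A subject troubled in this way may take the device off and not resume. If two hours of use is a condition for entering the AE tables, the event itself can cause the subject's exclusion, so membership of the analysis set depends on the outcome being measured. Such a rule can only reduce the count of subjects with an AE.

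AEs are part of the safety evidence in a study meant to support a PMA application (Protocol 6). Because the sections disagree, two analysts could each follow the plan and report different numerators and denominators.

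**Working it through.** No figure in the plan needs reproducing. The check sets the texts side by side and then scales the possible effect.

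**1. Who falls between the definitions.** Take a subject enrolled at power-ON who has a device-related AE and stops permanently after less than two hours of use.

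| Text | Is this subject's AE in the tables? |
|---|---|
| Protocol 12, Safety set and Adverse Events | No |
| SAP 8.2, all safety analyses on the Safety set | No |
| SAP 8.2, all other endpoints on ITT only | Yes |
| SAP 4.5, all reported AEs tabulated | Yes |
| SAP 8.3, withdrawn subjects' data in all analyses | Yes |
| SAP 6.1, listing of all AEs | Listed in any case |

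The Safety set selects subjects and is not a time window. An AE in the first two hours counts normally if the subject goes on to reach two hours.

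**2. Possible size (assumed illustration).** Inputs: 130 enrolled subjects (Protocol 8), and 6 of 32 pilot subjects with an AE (Protocol 6, Protocol 3335586). The number excluded, k, is not in the documents and is assumed.

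Expected subjects with an AE: 6/32 = 18.75%; 0.1875 × 130 = 24.4, taken as 24.

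Incidence if all k excluded subjects had an AE is (24 − k)/(130 − k). If none had, it is 24/(130 − k).

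| k | All k had an AE | None had an AE |
|---|---|---|
| 0 | 24/130 = 18.5% | 24/130 = 18.5% |
| 1 | 23/129 = 17.8% | 24/129 = 18.6% |
| 3 | 21/127 = 16.5% | 24/127 = 18.9% |

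**3. Range for the baseline rate.** The exact (Clopper-Pearson) 95% interval for 6/32 is 7.2% to 36.4%, or about 9 to 47 of 130 subjects. With k = 1 and that subject having an AE:
- low end: 9/130 = 6.92% becomes 8/129 = 6.20%, a fall of 0.72 points;
- high end: 47/130 = 36.15% becomes 46/129 = 35.66%, a fall of 0.49 points.

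The pilot enrolled people from the general population, not ICD patients, so its rate serves only for scale.

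**4. Medical Monitor wording (separate).** Protocol 9 and SAP 6.1 have the Monitor verify relatedness and seriousness for serious AEs. SAP 8.5 extends this to all such assessments for AEs. Protocol 12 describes the related-AE and severity summaries as resting on the Investigator's report with Monitor review, without limiting this to serious events. SAP 6.1 and 8.5 then let the Monitor's assessment replace the site's in the summaries. For a non-serious AE, it is unclear whether a Monitor assessment of relatedness and seriousness will exist to be tabulated.

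**The case against.** The strongest reply is that little can be lost. The two-hour rule is pre-specified and identical in both documents. SAP 6.1 lists all AEs and summarizes deaths and serious device-associated events. Protocol 9 requires an AE that causes withdrawal to be recorded, and Protocol 12 adds that "AEs leading to withdrawal from the study will be listed and tabulated". Nothing in the documents shows anyone stopping within two hours. Where the earlier studies give timing, skin irritation was seen after two or five days of wear, and shocks and shock alarms are off in this study. Secondary endpoints are exploratory and AEs carry no formal test.

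Most of this stands, and it limits the importance of the point. It does not remove the conflict: a listing does not supply the incidence table's numerator and denominator, and Protocol 12 does not say whether the withdrawal tabulation reaches subjects outside the Safety set.

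On the Monitor, it is fair to say that Protocol 9 already has every at least possibly related AE reviewed for UADE reportability. Since relatedness is part of this study's AE definition, the Monitor sees every AE. That is a different determination, however, and leaves the wording gap open.

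**Conclusion.** The point holds as an internal conflict over the AE population, with a possible outcome-dependent exclusion under one of the two readings. It is worth correcting because correction is cheap. It threatens no success criterion.

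A reader might infer more, and the documents do not support it:
- *That the tables will certainly omit early stoppers.* SAP 4.5, SAP 8.3 and the ITT sentence in SAP 8.2 say otherwise, so exclusion is one reading of an inconsistent plan.
- *That AEs in the first two hours are discarded, or that events vanish from the report.* Only subjects who never reach two hours are affected, and their AEs are still listed.
- *That the threshold refers to total use over the study.* Cumulative or continuous is not stated.
- *That AE incidence is known to be understated.* The number affected may be zero, and excluding subjects without an AE raises the percentage slightly.

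The fall of 0.5 to 0.7 points per excluded subject with an AE assumes 130 enrolled and a baseline rate anywhere in the pilot's exact interval. At the pilot's own rate, three such subjects would lower incidence from 18.5% to 16.5%.

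The Monitor wording is a separate, minor reconciliation.

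**What to change.** 1. **AE population.** Base the AE tables on all enrolled subjects (trained, fitted, connected, powered ON). Report separately how many had under two hours of use and which AEs they had, and state how the two hours are counted. Bring SAP 4.5, 8.2 and 8.3 into line with this.
2. **Monitor scope (minor).** Reconcile Protocol 9 and SAP 6.1 with SAP 8.5 and the Adverse Events paragraph of Protocol 12, so that it is clear whose assessment of relatedness and seriousness is tabulated for non-serious AEs.

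**Cost.** No new data are needed, because AEs are already collected from enrolment. Protocol 12 allows the SAP to define additional data sets, so item 1 can be done by SAP revision alone, with the protocol's Safety-set definition aligned at the next amendment. Until then, the Safety-set table that the protocol asks for can be shown beside the all-enrolled one. Item 2 is a wording change in the SAP, and in the protocol only if its text is the one altered. The revision should be approved before the primary endpoint is analyzed, as SAP 9 requires for planned changes. The downside for the sponsor is a possibly slightly less favourable AE count.
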